1.1 SYNOPSIS	
Title:	Development and validation of a digital pain-reduction kit for musculoskeletal injuries
Study Description:	This study will test the effectiveness of an evidence-based, multi-modal, "digital pain-reduction kit" as a non-pharmacological supplement to managing patients with pain due to musculoskeletal injuries. Outpatients will be randomized to receive either the pain reduction kit or an active control. The kit will contain a virtual reality (VR) headset, therapeutic VR visualization software, a low-cost wearable transcutaneous electrical nerve stimulation (TENS) unit. The control group will receive a TENS unit; they will not receive VR, or remote coaching. Study devices will be delivered to the patient's home with instructions for use; patients will receive remote clinical and technical support. Patients will be followed for 60 days and monitored for functional status, pain levels, use of pain medications (including opioids), satisfaction with care, and time to returning to work. Participants will also be asked to consent/authorization to access medical records from their treating facility (if a non-CSMC site).
Objectives:	Primary Objective: The primary objective of this study is to develop and validate a multi-modal digital pain reduction kit for improving physical function over time. Secondary Objective: The secondary objective of this study is to investigate the efficacy of a multi-modal digital pain reduction kit in reducing pain interference over time, work productivity, opioid use, and satisfaction with care.
Endpoints:	Primary Endpoint: The primary outcome measures in this study are weekly surveys (PROMIS® PF short-form) of self-reported physical function. Secondary Endpoints: The secondary outcome measures in this study are pain interference (PROMIS® Pain Interference), work absenteeism and presenteeism (WPAI:LB), number of 90 Morphine Milligram Equivalent opioid prescriptions, and satisfaction with healthcare (Pain Treatment Satisfaction Scale and SF Patient-Satisfaction Questionnaire).
Study Population:	The study consists of 174 English adults (75 intervention; 75 control with TENS; 24 control without TENS) in the Greater Los Angeles Area presenting with pain from musculoskeletal injuries.
Phase:	N/A
Description of	Cedars-Sinai Medical Center Orthopedic Clinic
Sites/Facilities Enrolling	Cedars-Sinai Medical Delivery Network (MDN)
Participants:	Medical College of Wisconsin (MCW)
Description of Study Intervention:	Participants assigned to the control arm will receive standard of care, TENS unit. Participants assigned to the intervention will receive standard of care, plus the following study components: - Virtual reality headset with integrated video experiences (3x daily)

	 Transcutaneous electrical nerve stimulation unit for pain reduction (used as needed) Remote clinical and technical support (opt-in, then health coach- initiated)
Study Duration:	16 months
Participant Duration:	60 days

1.3 SCHEDULE OF ACTIVITIES (SOA)

Procedures	Screening Day -7 to -1	Visit 1, Day 1	Day 7 +/-1 day	Day 14 +/- 1 day	Day 21 +/-1 day	Day 28 +/-1 day	Day 35 +/-1 day	Day 42 +/-1 day	Day 49 +/-1 day	Day 56 +/-1 day	Final Study Visit 2 Day 60 +/-1 day
Informed consent	Х										
Demographics	Х										
Medical history	Х										
Randomization	Х										
EHR data (opioid use)		Х									Х
Administer study intervention kits		Х									
Intervention (Virtual reality)		Х	Х	Х	Х	Х	Х	Х	Х	Х	Х
Intervention (TENS)		Х	Х	Х	Х	Х	Х	Х	Х	Х	Х
PROMIS [®] questionnaires		х	х	х	х	х	х	х	Х	х	Х
Assess absenteeism and presenteeism (WPAI)		Х									х
Satisfaction with pain treatment and healthcare											Х
Collect VR compliance data		Х									Х
Remote clinical and/or technical support X				Х							
Collect study intervention kits											Х

Note: Participants will only have two site visits, the SoA illustrates additional days for remote measurement. Site visit days are labeled as "Visit 1" and "Visit 2."

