3 OBJECTIVES AND ENDPOINTS

OBJECTIVES	ENDPOINTS	JUSTIFICATION FOR ENDPOINTS
Primary		
The primary objective of this study is to develop and validate a multi- modal digital pain reduction kit for improving physical function over time.	The primary endpoint in this study is a clinically significant change in self- reported physical function over time among individuals in the intervention arm compared to those in the active control. The outcome measure used to quantify this endpoint is the PROMIS® PF short-form, a validated self-report of physical function. The	The PROMIS® PF short- form scale is a widely validated instrument with excellent content validity, construct validity, and reliability in patients with spinal disorders and other conditions marked by

OBJECTIVES	ENDPOINTS	JUSTIFICATION FOR ENDPOINTS
	outcome measure is administered on a weekly basis via a smartphone survey to capture longitudinal change and variation among participants.	diminished mobility. The outcome measure allows us to place patients on a continuum of physical function with respect to various physical actions.
Secondary		
The secondary objective of this study is to investigate the efficacy of a multi-modal digital pain reduction kit in reducing pain interference over time, work productivity, opioid use, and satisfaction with care.	The secondary endpoints of are clinically significant changes in pain interference, work productivity, use of opioids, and satisfaction with healthcare among those in the intervention arm compared to participants in the active control. Outcome measures include pain interference (PROMIS® Pain Interference, measured weekly via smartphone surveys), work absenteeism and presenteeism (WPAI:LB, measured at baseline and exit surveys), number of 90 Morphine Milligram Equivalent opioid prescriptions (obtained via cumulative EHR records), and satisfaction with healthcare (CG- CAHPS, measured once at the conclusion of the study).	
Tertiary/Exploratory		
N/A	N/A	N/A

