5 STUDY POPULATION

5.1 INCLUSION CRITERIA

In order to be eligible to participate in this study, an individual must meet all of the following criteria:

- 1. Provision of signed and dated informed consent form
- 2. Stated willingness to comply with all study procedures and availability for the duration of the study
- 3. Male or female, aged 18 or older
- 4. Seeking care for a musculoskeletal injury
- 5. Experiencing pain greater than 3 out of 10 on a visual analog scale
- 6. English speaking
- 7. Owns a compatible Android or iOS smartphone device (excluding tablets)

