6.2 MEASURES TO MINIMIZE BIAS: RANDOMIZATION AND BLINDING

Per the new protocol, participants will be randomized intervention or control until intervention and control groups each have 75 enrollees. In addition to these 150 participants, the group of 24 controls that were originally recruited without the TENS unit will remain accounted for in the supplementary analysis. There will be no blinding, as participants in the control group will be aware that they are missing components of the intervention as detailed in the consent form.

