9.4.2 ANALYSIS OF THE PRIMARY EFFICACY ENDPOINT(S)

Statistical Analyses: Data for Aim 1 are repeated-measures data and will not support bivariate analysis by Pearson and/or Spearman correlations, as autocorrelation can cause transient or spurious relationships with high correlations for some periods and none for others. Similarly, for a linear regression model, this type of data may cause residuals for the same individual to be correlated. Therefore, we will employ linear mixed models featuring fixed effects and random effects (i.e. random intercepts) to account for within subject variation. We will also perform a differences-in-differences analysis comparing change between baseline and the end of the intervention to determine which strategy resulted in greater improvement in PF.

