9.4.4 ACCOMODATING ADDITION OF TENS UNIT TO THE CONTROL ARM

An ITT analysis "Includes all randomized patients in the groups to which they were randomly assigned, regardless of their adherence with the entry criteria, regardless of the treatment they actually received, and regardless of subsequent withdrawal from treatment or deviation from the protocol."^{ref} Accordingly, we will follow the original analysis plan described above with regard to analyzing results by study-arm. In addition to the ITT analysis, however, we will conduct a sensitivity analysis by repeating the statistical procedures in a per-protocol fashion wherein the members of the control arm who did not receive a TENS unit will be dropped from the sample. Directions, magnitudes, and significance of treatment effects will be presented for both analyses.

Furthermore, because the TENS unit will appear in both study arms - and unevenly in the control arm – we recognize that an ITT analysis strictly *by* study-arm risks misidentifying the effect of treatment, while a per-protocol analysis risks introduction of bias. Therefore, we will conduct an additional linear mixed model regression analysis using a term for the TENS that captures the effect of the TENS separately from the effects of study-arm assignment. The model used to fit these data is as follows:

 $\hat{y}_{it} = \beta_0 + \beta_1 time_{it} + \beta_2 study_arm_{it} + \beta_3 TENS_{it} + e_{it}$

where time represents change in time from baseline, study_arm indicates status as a control or experimental participant (0= control and 1=experimental), *i* is the individual participant, and TENS indicates TENS unit usage (0= no TENS unit and 1=TENS unit). We can therefore write a regression equation describing each type of patient differentiated by the addition of the TENS unit to control conditions:

Treatment: $\hat{y}_{it} = \beta_0 + \beta_1 time_{it} + \beta_2 study_arm_{it} + \beta_3 TENS_{it} + e_{it}$

Control w/o TENS: $\hat{y}_{it} = \beta_0 + \beta_1 time_{it} + e_{it}$

Control w/ TENS:

 $\hat{y}_{it} = \beta_0 + \beta_1 time_{it} + \beta_3 TENS_{it} + e_{it}$

In this manner we isolate the term of interest (study_arm). Given we are only adding one term but 20 subjects, we are comfortable relying on the original power calculation.

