10.1.3 CONFIDENTIALITY AND PRIVACY

Participant privacy is strictly held in trust by the participating investigators, their staff, and their interventions. Therefore, the study protocol, documentation, data, and all other information generated will be held in strict confidence. No information concerning the study or the data will be released to any unauthorized third party without prior written approval of the sponsor.

Individuals viewing private and identifiable information, such as physicians, are reasonably expected to be viewing such information whether participants were enrolled in the study. All research activities will be conducted in closed-door, private room during initial contact and subsequent follow-up. The setting for much of the study will be at the participant's discretion, as only two visits (baseline and exit) are made during before and after the intervention period.

Representatives of the Institutional Review Board (IRB) or regulatory agencies may inspect all documents and records required to be maintained by the investigator for the participants in this study. The clinical study site will permit access to such records as needed.

Data in the study is collected in three ways: in real-time, at infrequent intervals throughout the study, and through medical record queries. Real-time data, including biometrics and survey data delivered via mobile device, will be stored on secure servers hosted by Amazon Web Services (AWS) and will contain only a unique identifier for each participant. Virtual reality adherence data will also be tracked in real-time and hosted on secure servers by AppliedVR; a separate unique ID will be assigned to each participant. Data collected at infrequent intervals throughout the study, such as entry, weekly, and exit questionnaires will be stored on secure CSMC servers with unique ID's for each participant. Data collected from medical record numbers, such as opioid prescriptions and physician history, will reside on secure CSMC servers and an ID will be assigned to each individual in order to abstract PHI/PII and the medical record number. Each dataset will utilize different unique ID's and a list linking each unique ID to each participant will be stored internally on the secured CSMC network. The linking list allows a researcher with access to the secured files to merge all data using statistical software, while maintaining data confidentiality.

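### Randomisation is scheduled before the first PROMIS and WPAI surveys, and nothing in this unblinded plan withholds the allocation until those baseline surveys are submitted

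*Combined protocol and SAP*

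**What the plan says.** In 1.3 the randomisation row has one mark, in the column "Screening Day -7 to -1", alongside consent, demographics and medical history. The PROMIS and WPAI rows are empty there. Both start at Visit 1, Day 1, where the kits are also handed over. PROMIS then runs weekly to Day 56 and again at Day 60; WPAI is repeated only at Day 60. The endpoint table in section 3 describes WPAI as "measured at baseline and exit surveys", so Day 1 is the baseline. Section 4.1 limits WPAI to patients with lower back pain.

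On blinding, 6.2 says: "There will be no blinding, as participants in the control group will be aware that they are missing components of the intervention".

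On use of the baseline, 9.4.2 plans a mixed model with random intercepts and also a difference-in-differences analysis "comparing change between baseline and the end of the intervention to determine which strategy resulted in greater improvement in PF". Section 9.4.3 repeats that comparison for the secondary endpoints, and 9.1 lists baseline PROMIS scores among the potential covariates.

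The only symptom score needed before randomisation is the eligibility criterion in 5.1: "Experiencing pain greater than 3 out of 10 on a visual analog scale".

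**The concern.** Randomisation makes the arms comparable on anything measured before it, or measured afterwards without knowledge of the arm. A questionnaire answered once the participant knows which arm they are in has neither protection. A control participant disappointed at not receiving the headset might rate function lower on Day 1; a participant holding the headset might rate it higher. If that reaction fades by Day 60, the change from baseline carries it with the opposite sign and the comparison of changes is biased.

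At stake are the difference-in-differences for physical function and for the secondary scores with a Day 1 value, any model adjusted for baseline PROMIS, and WPAI, which has only two occasions. Opioid data from health records and satisfaction scores taken only at exit are not affected.

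**Working it through.** **Step 1: does any section supply the missing rule?** The plan gives no figure to reproduce here, so the first check is a reading check.

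- 4.1 names a random number generator and 6.2 gives the target of 75 per arm. Neither says when the arm is disclosed.
- The note to 1.3 says "Participants will only have two site visits", and 10.1.3 says "only two visits (baseline and exit) are made during before and after the intervention period". These place the baseline visit before the intervention, not before randomisation or disclosure.
- 5.5 sends equipment by courier to those who consent remotely. 10.1.1.2 requires signed consent before materials are delivered; it does not require completed surveys.

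No rule was found. Disclosure before the Day 1 survey is therefore possible under the plan, and neither stated nor excluded.

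**Step 2: what would a shift do?**

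Inputs from the documents: PROMIS on Days 1, 7, 14, 21, 28, 35, 42, 49, 56 and 60, ten occasions (1.3); 10 T points = 1 SD and MCID = 2 points (8.1); design effect 0.6 SD = 6 points and 25% withdrawal (9.2); 75 per arm (6.2).

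Assumptions, none of them from the documents: s is the kit-minus-control reporting shift in physical function, present on Day 1 only; the correlation rho of baseline with Day 60 is 0.4 to 0.8 with equal SDs; the intraclass correlation is 0.4 to 0.8; withdrawal is spread evenly over follow-up.

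- Difference-in-differences: (Day 60 difference) - (Day 1 difference) is biased by 0 - s = -s.
- Day 60 comparison adjusted for baseline: bias -rho × s, that is -0.4s to -0.8s.
- Arm main effect in a random-intercept model without an arm-by-time term, the form written out in 9.4.4: with complete data it is the difference in means over ten occasions, so the bias is s/10 = +0.10s. With 25% withdrawal, generalised least squares gives +0.135s (intraclass correlation 0.4) to +0.148s (0.8).
- Arm-by-time slope over 59 days, only if such a term were fitted, which the documents do not write out: mean day 313/10 = 31.3, sum of squares 3800.1, so 59 × (1 - 31.3)/3800.1 = -0.47s with complete data.
- WPAI, Days 1 and 60, own units: difference-in-differences -s; main effect s/2 = +0.5s, or about 0.59s to 0.62s if 25% have Day 1 only.

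Absolute bias in physical function, T points:

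| Assumed s | Difference-in-differences | Baseline-adjusted | Arm main effect |
|---|---|---|---|
| 0.5 | 0.5 | 0.2 to 0.4 | 0.05 to 0.07 |
| 1 | 1.0 | 0.4 to 0.8 | 0.10 to 0.15 |
| 2 | 2.0 | 0.8 to 1.6 | 0.20 to 0.30 |

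At s = 1 the difference-in-differences moves by 1/6 = 17% of the design effect; the arm main effect moves by 0.10/6 to 0.148/6, about 1.7% to 2.5%. The first result needs the shift only to be gone by Day 60. The arm main effect figure needs it gone by Day 7; a shift lasting over k of the ten surveys gives k × s/10 with complete data.

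**Step 3: could it be seen afterwards?** Day 1 arm means can be compared. The standard error is 10 × sqrt(2/75) = 1.63 points, so a 95% interval spans about ±1.96 × 1.63 = ±3.2 points, wider than the MCID. Such a comparison also cannot separate chance imbalance from a reporting shift.

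**The case against.** The strongest reply is that the concern rests on silence. The schedule records when randomisation happens, not when participants are told, and the Day 1 surveys may in practice be completed first. That is correct. A reader might infer that participants did report their baseline knowing their arm; the documents do not support that.

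Two features may also limit any effect. PROMIS uses a 7-day recall (8.1), so the Day 1 answer mostly describes the week before the kit. The control is active and was chosen partly to limit reactivity (4.2), so current controls also receive a device. Both are mitigating. Neither removes the issue: the answer is still given on Day 1, and the 24 earlier controls had no TENS unit (4.1).

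It can further be said that moving the baseline might increase the bias. If a fraction f of the shift persists to Day 60, the bias of the change comparison goes from -(1 - f)s now to +f × s with a baseline taken before randomisation. In absolute size that is 0.75s to 0.25s at f = 0.25, but 0.25s to 0.75s at f = 0.75. The arithmetic is right, and no document gives f. But the present order does better at high f only because two reporting biases happen to cancel. A protected baseline leaves one bias, at follow-up, that an open-label trial has in any case.

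**Conclusion.** The point holds as a gap in the plan: the stated order leaves the self-reported baseline unprotected, and no rule closes the gap. It should be corrected, but it does not invalidate the trial.

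Three stronger conclusions are not supported. First, that the kit's benefit would be exaggerated: on the mechanism described, the difference-in-differences would understate it. The opposite direction is equally undocumented and would overstate it. Second, that the whole primary analysis is compromised: an arm main effect barely moves if the shift is confined to Day 1. The two analyses estimate different things and can disagree without bias; a Day 1 shift would be one further reason for disagreement. Third, that the problem could never be checked: Day 1 arm means give a partial, imprecise check.

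Every size above scales with s, for which the documents give neither magnitude nor sign. A 1-point shift is smaller than the standard error of a mean difference in one trial (1.63 points at 75 per arm; 10 × sqrt(2/56) = 1.89 at 56 per arm, from 0.75 × 75). Unlike sampling error, however, a systematic shift does not shrink with more participants.

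**What to change.** For participants still to be enrolled, amend 1.3 so that baseline PROMIS and, where applicable, WPAI are completed after consent and before randomisation. If that is not feasible, require them to be submitted before the allocation is disclosed and before equipment is handed over or opened. Define that score as the baseline in 9.4.2 and 9.4.3, and state when participants learn their arm.

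For participants already enrolled, flag the baseline as collected after randomisation, and add a sensitivity comparison of the arms at Day 60 without baseline adjustment.

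The surveys can be sent by email (8.1), so no visit is added. The costs are:

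- The baseline may precede the kit by up to about 7 days.
- Those who do not complete the survey are not randomised or, under the fallback, receive equipment late. This matters because the summary of changes reports withdrawals from low survey compliance.
- The trial would hold two baseline definitions, separated by calendar time.
- The unadjusted Day 60 comparison is less precise: standard error 1.89 points at 56 per arm, against 1.89 × sqrt(1 - rho²) = 1.73 (rho 0.4) or 1.51 (rho 0.6) with adjustment.

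Reporting bias at follow-up in an open-label trial is not addressed by this change.

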2 INTRODUCTION

2.1 STUDY RATIONALE

The aim of this randomized, controlled trial (RCT) is to assess the relative benefits of using a digital pain-reduction kit (including virtual reality unit, transcutaneous electrical nerve stimulation unit, and remote clinical support) for pain management outcomes – including functional status, pain interference, work productivity and activity impairment, usage of pain medication, and satisfaction scores in a cohort of patients with pain related to musculoskeletal injuries.

2.2 BACKGROUND

Pain from musculoskeletal injuries is a prevalent and expensive condition that negatively impacts health related quality of life (HRQOL), diminishes functional status, and leads to a high rate of work absenteeism. Some patients with musculoskeletal injuries, including lower back pain, turn to opioids, a class of medications that may provide effective analgesia but can lead to opioid use disorder, opioid-related overdoses and serious adverse events, including death. The average time lost for workers using opioids can total as much as \$117,000 per insurance claim – a value that is 900% higher than the cost of claims for workers who do not take opioids. From both a clinical and health economic perspective, it is vital to identify opioid-free treatments to assist in the management of pain caused by musculoskeletal injuries.

2.3.1 KNOWN POTENTIAL RISKS

Short-term risks associated with the study may include minor psychological distress from questionnaires regarding health and employment status, acute virtual reality discomfort (e.g., headache, vertigo, nausea), and minor side effects from transcutaneous electrical nerve stimulation (e.g., muscle twitching, muscle soreness, skin irritation). There are no anticipated long-term risks from participating in this study.

Participants may elect to receive standard of care in lieu of participation in the study.

There are some risks associated with the electronic collection and transmission of protected health information for the purpose of research. Unanticipated breaches of data may result in exposure of confidential information to individuals outside of study staff.

